8.3.4 Conjunctival Lissamine Staining

Conjunctival lissamine staining will be conducted by the Investigator and assessed after corneal fluorescein staining. For individual subjects, lissamine staining should be assessed by the same examiner at all visits using the same slit lamp and the same settings. The right eye should be completed first, followed by the left eye.

Lissamine impregnated strips supplied by the sponsor will be used according to package instructions. One drop of sterile saline, or equivalent, will be applied to the tip of the strip. DO NOT use anesthetic drops to wet the strips. Immediately after application of the wetting drop to the strip, gently flick the excess drop off the end of the strip prior instilling the dye. A new strip should be used for each eye.

The degree of staining is based on the Lissamine Conjunctival Oxford Staining Scale. The nasal and temporal conjunctival regions are assessed for interpalpebral lissamine conjunctival staining (the corneal region must not be assessed). Each of the two regions (as depicted in the diagram) will be graded on a scale of 0 to 5 (Figure 8-3). The examiner will indicate the appropriate score for each region. If the assessment falls between grades, round up to the higher score. After entry of the scores per region, the total or composite (sum) score for each eye will be automatically calculated (maximum score = 10/eye).

Equal to or less 0 than panel A Equal to or less I than panel B, greater than A Equal to or less I than panel C, greater than B Equal to or less III than panel D, greater than C Equal to or less IV than panel E. greater than D Greater than ٧ >E panel E

Figure 8-3 Lissamine Conjunctival Oxford Staining Scale

8.3.5 Appropriateness of efficacy assessments

The efficacy assessments included in this study for the evaluation of ocular signs and symptoms are commonly used in clinical research for DED and are accepted methods for evaluation of drugs for market authorization by the US FDA.

8.4 Safety

Safety assessments are specified below with the assessment schedule detailing when each assessment is to be performed.

For details on AE collection and reporting, refer to Section 10 (Safety monitoring and reporting).

Table 8-3 **Assessments & Specifications**

Assessment	Specification
Corrected Visual Acuity	Qualified site personnel will conduct Snellen visual acuity testing in each eye separately per standard clinical practice and should precede any examination requiring administration of eye drops to dilate the eye or any examination requiring contact with the eye.
	Subjects must use their standard prescribed correction or pin hole. No refraction will be conducted at the visit to determine best correction.
Slit Lamp Exam	The Investigator will perform a slit-lamp assessment of the anterior portion of the eye of both eyes before instillation of any diagnostic eye drops, including evaluation of the lids, cornea, conjunctiva, iris, anterior chamber, and lens.
Intraocular Pressure	Intraocular pressures will be measured in both eyes by a qualified technician and according to the study site's regular practice. The same method must be used throughout the study for both eyes in each subject.
Fundus Exam	The Investigator will perform an ophthalmoscopic examination of the posterior segment of both eyes including the vitreous, retina, macula, choroid and optic nerve. Dilation can be performed at the Investigator's discretion.

8.4.1 Laboratory evaluations

Not Applicable.

8.4.2 Pregnancy

A urine pregnancy test will be conducted for all women of childbearing potential to assess pregnancy as indicated in the Schedule of Assessments.

Additional pregnancy testing might be performed if requested by local requirements.

8.4.3 Appropriateness of safety measurements

The safety assessments selected are standard for this indication/subject population.

8.5 Additional assessments

8.5.1 Clinical Outcome Assessments (COAs)

Subject questionnaires should be completed in the language most familiar to the subject, and given sufficient time to complete the questionnaires truthfully and accurately.

Confidential

For questionnaires completed by the subject in the clinic, the site personnel should check PRO measures for completeness and ask the subject to complete any missing responses. The responses that are stored electronically in the database will be considered the source file.

Completed measures and any unsolicited comments written by the subject should be reviewed and assessed by the investigator for responses which may indicate potential AEs or SAEs before any clinical study examinations. This assessment should be documented in study source records. If AEs or SAEs are confirmed, study investigators should not encourage the subject to change responses reported in the completed questionnaires. Study investigators must follow reporting instructions outlined in Section 10 (e.g. reference "Adverse Events" section) of the study protocol.

Site personnel should monitor a subject's compliance with completion of the daily diary. If the subject is not compliant with diary entries, the reason for the non-compliance should be determined and corrective efforts should be made. If the subject is repeatedly unable to comply with the daily diary requirements, the subject should be considered not appropriate for the study due to inability to follow protocol requirements, and should be discontinued.

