4.6 Rationale for Public Health Emergency mitigation procedures

During a Public Health emergency as declared by Local or Regional authorities i.e. pandemic, epidemic or natural disaster, mitigation procedures to ensure subjects afety and trial integrity are listed in relevant sections. Notification of the Public health emergency should be discussed with Novartis prior to implementation of mitigation procedures, and permitted/approved by Local or Regional Health Authorities and Ethics Committees as appropriate.

5 Population

This study will enroll adult subjects, 18 years of age or older with at least 6 months history of physician diagnosed moderate to severe dry eye disease in both eyes as defined by entry criteria.

It is estimated that approximately 800 subjects will need to be screened in Part 1 to have approximately 680 subjects randomized into the 56-day treatment period. Enrollment in the study will remain open until a sufficient number of evaluable subjects is achieved in Part 1.

For Part 2, it is estimated that up to 200 subjects will need to be screened to randomize up to 160 subjects into the 2 treatment arms.

Subjects discontinuing the study after randomization in either Part 1 or Part 2 will not be replaced, and subjects who discontinue the study in Part 1 will no longer be eligible for Part 2.

For subjects who discontinue treatment but do not discontinue the study during Part 1, or for subjects who experience a treatment related adverse event (AE) or serious adverse event (SAE), eligibility for Part 2 will be dependent on the reasons for treatment discontinuation or nature of the AE/SAE. The decision for participation in Part 2 will be at the discretion of the Investigator, with guidance from the Sponsor as needed.

The following inclusion/exclusion criteria apply to screening of subjects in Part 1, as well as screening and baseline in Part 2.

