Only subjects assigned exclusively to vehicle treatment in Part 1 may be eligible to participate in Part 2 of the study. A list of subjects eligible for screening in Part 2 of the study will be discussed between the Investigator and the Sponsor prior to initiating screening visits. In the event a study site was initiated close to the end of enrollment and did not have sufficient time to begin recruiting subjects in Part 1, the site may enroll subjects into Part 2 of the study if approved by the Sponsor.

Subjects are encouraged to stick to the scheduled visits as much as possible. If a subject is unable to return to the site as per the visit schedule, no visits should be missed, and efforts should be made to resupply the subject with sufficient drug (as needed). Subjects should be seen for all visits/assessments as outlined in the assessment schedule (Table 8-1 and Table 8-2) as close as possible to the target visit day and as close to the same time of day for each visit as possible. If a subject returns to the site for a visit earlier or later than planned, the next sequential visit should take place. The remaining subsequent visits should then be scheduled in a way that

brings the subject back to their original target dates for each visit as determined at Screening/Baseline.

Subjects must not have dosed with study medication within 4 hours of the visit assessments being conducted.

Missed or rescheduled visits should not lead to automatic discontinuation.

Subjects who prematurely discontinue the study for any reason should be scheduled for a visit as soon as possible, at which time all of the assessments listed for the final visit will be performed. At this final visit, all dispensed investigational product must be reconciled, and the adverse event and concomitant medications recorded on the eCRF.

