Period Treatment Screening Visit Name Visit 1-Screening Visit 2 Visit 3 Visit 4 Visit 5/EOS Visit 1-Randomization 28 Days 1 14 42 56 1 Informed consent Х Х Inclusion / Exclusion criteria Demography Х Medical history/current medical conditions X Concomitant medications Х Х Х Х Х Pregnancy Test (urine) Х Х Х In office SANDE score Х Corrected visual acuity Х Х Х Х х Х Х х Х Slit lamp biomicroscopy Х Ocular hyperemia Х Х Х Х Tear break-up time (TBUT) Х Х Х Х Х х Corneal fluorescein staining² Х Х Х Х Х Х Х Х Х Conjunctival lissamine staining Schirmer Tear Test Х Intraocular Pressure (IOP) Х Х Х Х Х Fundus Exam Х Х Contact IRT³ Х Х Х Х Randomization Х Dispense study medication Х Х Х Х Х In-office study drug administration

Table 8-1 **Assessment Schedule, Part 1**

Novartis	Confidential	
Amended Protocol Version 01 (Clean)		Pro

Page 39 Protocol No. CECF843A2201

Period	Screening	Treatment						
Visit Name	Visit 1-Screening	Visit 1-Randomization	Visit 2	Visit 3	Visit 4	Visit 5/EOS		
Days	1	1	14	28	42	56		
Adverse Events	Х	x	Х	Х	Х	Х		
At home SANDE questionnaire (eDiary) ⁴	Х		Х	Х	Х			
Study completion information						Х		
X Assessment to be recorded in the clinica	l database or received e	ectronically from a vendor			•	÷		

3 Sites will enter average SANDE score (obtained from the electronic diary) and the corneal fluorescein staining score from the eye with the highest composite score (sum of the 5 regions)

4 Subjects will complete an electronic diary once daily (in the evening before bed time and prior to the evening dose of study medication) from Visit 1-Screening through to the end of the study (at home SANDE questionnaire)

Table 8-2Assessment Schedule, Part 2

Period	Screening	Treatment	eatment						Post Treatment Follow-up		
Visit Name	Visit 1	Visit 2	Visit 3	Visit 4	Visit 5	Visit 6	Visit 7/ EOT	Visit 8/ EOS ⁸	Safety F/U EOS ⁸ +4. +8, +12 Weeks		
Days	-14	1	7	14	28	42	84	126	154, 182, 210		
Informed consent	х										
Inclusion / Exclusion criteria	x	x									
Demography	Х										
Medical history/current medical conditions	x										
Concomitant medications	x	x	x	x	x	x	x	x	x		
Pregnancy Test (urine)	Х						X				

Period	Screening	Treatment						Post Treat	tment Follow-up
Visit Name	Visit 1	Visit 2	Visit 3	Visit 4	Visit 5	Visit 6	Visit 7/	Visit 8/ EOS ⁸	Safety F/U EOS ⁸ +4. +8, +12 Weeks
Days	-14	1	7	14	28	42	EOT 84	126	154, 182, 210
In office SANDE score	X	X		14	20	72	04	120	134, 102, 210
Corrected visual acuity		Х					Х		
				.					

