8.3.3 Corneal Fluorescein Staining

Corneal fluorescein staining will be conducted by the Investigator. For individual subjects, corneal fluorescein staining should be assessed by the same examiner at all visits using the same slit lamp and the same settings. The right eye should be completed first, followed by the left eye.

[figure not shown]
At visits where TBUT is also done, instillation of the sodium fluorescein dye will have already occurred. As long as the corneal staining assessment is done within the specified time frame, no additional instillation of fluorescein dye is required. At visits where TBUT is not done, follow the same procedure as described above for instillation of fluorescein dye to each eye.

Staining will be assessed a minimum of 2.5 minutes and preferably less than 5 minutes after instillation of the dye. Evaluation of the cornea will be done through a slit lamp with use of a cobalt blue filter.

The degree of staining is based on the Corneal Fluorescein Modified NEI Scale. Each of the five regions (as depicted in the diagram, and defined as central (C), superior (S), inferior (I), temporal (T), and nasal (N)) will be graded based on a scale of 0 to 4, with higher scores suggestive of higher degrees of corneal staining (Figure 8-2). The examiner will indicate the appropriate score for each region. If the assessment falls between grades, round up to the higher score. After entry of the scores per region, the total or composite (sum) score for each eye will be automatically calculated (maximum score = 20/eye).

A (+1) will be added to the sum score for any eye with the presence of filaments.

Figure 8-2 Corneal Fluorescein Modified NEI Scale

Grade 0	No staining
Grade 1	Superficial micropunctate staining covering < 25% of the corneal surface
Grade 2	Macropunctate staining AND/OR superficial micropunctate staining covering 25-50% of the corneal surface
Grade 3	Some coalesced macropunctate staining AND/OR superficial micropunctate staining covering 51-75% of the corneal surface
Grade 4	Numerous coalesced macropunctate areas and/or patches AND/OR superficial micropunctate staining covering > 75% of the corneal surface

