9.1 Discontinuation

9.1.1 Discontinuation of study treatment

Discontinuation of study treatment for a subject occurs when study treatment is permanently stopped for any reason (prior to the planned completion of study drug administration, if any) and can be initiated by either the subjector the investigator

Discontinuation from study treatment is required under the following circumstances:

- Subject/guardian decision
- Pregnancy
- Use of prohibited treatment as per recommendations in the prohibited treatment section (see Section 6.2.2)
- Any situation in which continued study participation might result in a safety risk to the subject
- Inability or unwillingness of the subject to follow the protocol requirements
- Following emergency unblinding (see Section 6.6.3)
- Adverse events that indicate a safety risk to the subject
- Unsatisfactory therapeutic effect

If discontinuation from study treatment occurs, the investigator should make a reasonable effort to understand the primary reason for the subject's premature discontinuation of study treatment and record this information.

Subjects who discontinue from study treatment agree to return for the end of treatment and follow-up visits indicated in the Assessment Schedule (refer to Section 8).

If the subject cannot or is unwilling to attend any visit(s), the site staff should maintain regular telephone contact with the subject, or with a person pre-designated by the subject. This telephone contact should preferably be done according to the study visit schedule.

After study treatment discontinuation, at a minimum, in abbreviated visits, the following data should be collected at clinic visits or via telephone/email contact:

- New / concomitant treatments
- Adverse Events / Serious Adverse Events

The investigator must also contact the IRT to register the subject's discontinuation from study treatment.

If discontinuation occurs because treatment code has been broken, please refer to Emergency breaking of treatment code section.

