12.4.3 Handling of intercurrent events of primary estimand

The primary estimands will be the treatment effect of ECF843 against its corresponding vehicle, had subjects not taken artificial tears/gels/lubricants or prohibited medications as described in Section 6.2.2, and had they stayed on study treatment for the whole study duration. The hypothetical strategy assumes the subjects with intercurrent events (IEs) will behave like other subjects who did not take rescue/prohibited medications and stayed on study treatment. The primary analysis will account for different IEs as following:

- 1. Use of artificial tears/gels/lubricants: For subjects who use artificial tears/gels/lubricants occasionally for rescue, the data on the day(s) will be excluded and treated as missing.
- 2. Use of prohibited medications:
- For subjects who took ocular, nasal, inhaled, or systemic corticosteroids, intravitreal injections of any kind, the data on the day(s) + 3 days following the last day of prohibited medications will be excluded and treated as missing.
- For subjects who took the following prohibited medications,
 - Any topical ocular medications (prescription or over the counter; excluding IOP-lowering medication)
 - Medical device treatments such as those used to treat Meibomian gland dysfunction (eg, LipiFlow, pulse light therapy, etc)
 - Punctal plugs or punctal cauterization
- The data on the day(s) of prohibited medications will be excluded and treated as missing.
- 3. Discontinuation of study treatment for any reason: For subjects who discontinue study treatment, the data collected following the discontinuation will be excluded and treated as missing.

Missing data will be implicitly imputed under Missing at Random (MAR) assumption for MMRM analysis, that is missing data are imputed based on the treatment-specific information for the repeated measurements at baseline and post-baseline days/visits.

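### Stopping treated subjects for repeated missed diary entries also removes their later on-treatment corneal staining from the primary analysis, a loss the plan could avoid cheaply

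*Protocol*

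**What the plan says.** **The diary rule.** Protocol 8.5.1 asks sites to monitor diary completion, establish the reason for non-compliance and try to correct it. If the subject still repeatedly fails, "the subject should be considered not appropriate for the study due to inability to follow protocol requirements, and should be discontinued". The section does not define repeated failure, and does not separate stopping treatment from leaving the study.

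**What a stop entails.** Protocol 9.1.1 lists the circumstances in which study treatment must be discontinued. One is "Inability or unwillingness of the subject to follow the protocol requirements". These subjects are expected to return for the end-of-treatment and follow-up visits. The floor is lower: "After study treatment discontinuation, at a minimum, in abbreviated visits, the following data should be collected at clinic visits or via telephone/email contact", followed by two items only, concomitant treatments and adverse events. If the subject leaves the study instead, Protocol 8 asks for one early final visit with the final-visit assessments.

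**What the analysis does.** Protocol 12.4.3 says: "For subjects who discontinue study treatment, the data collected following the discontinuation will be excluded and treated as missing". SAP Table 2-4 repeats this, and both rely on missing at random (MAR) within the mixed model. The rule covers SANDE and composite corneal staining alike.

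**Where staining comes from.** Protocol 8.3.3: "Corneal fluorescein staining will be conducted by the Investigator". It is graded at the slit lamp in clinic, and nothing in the procedure uses the diary.

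**How the plan treats poor diaries elsewhere.** Under SAP 2.1.1.7 a missed evening is a missing SANDE day. Protocol 12.4.4 handles intermittent gaps under MAR. SAP Table 5-1 (deviation OTH11) keeps subjects with SANDE compliance below 50% in all analysis sets.

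**The concern.** The two primary endpoints are measured independently of each other. A subject who fails at the diary can still attend clinic and have the cornea graded. The rule turns failure on one endpoint into loss of the other, and it gains nothing for SANDE, since missed days cannot be entered later and any further partial entries drop out as well.

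The loss falls after randomization and depends on how each site reads repeated failure. Whether diary failure is related to outcome is unknown. If it is, MAR assumes that stopped subjects would have fared like similar subjects who stayed. No sensitivity analysis of the primary estimand is planned (Protocol 12.4.5 and SAP 2.5.4.2 both say not applicable).

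**Working it through.** **1. Does the chain hold under both readings?** If 8.5.1 means treatment, 9.1.1 requires the stop and 12.4.3 excludes the later data. If it means study, later staining beyond one early final visit is not collected. Either way, later on-treatment staining leaves the primary analysis.

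**2. How many visits?** Part 1 visits fall on Days 14, 28, 42 and 56 (Protocol Table 8-1), 14 days apart. The primary staining model uses post-baseline visits on treatment (Protocol 12.4.2), which SAP 2.5.2 gives as randomized study treatment. ECF843 exposure is at most 28 of the 56 days (Protocol 3). A 28-day block that starts at a visit contains 28/14 = 2 later visits. So an ECF843 subject can lose at most two such visits, and fewer if stopped part-way. Which visits count is not visible in the public SAP. A stop after the last counted visit costs the primary analysis nothing.

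**3. The plan's own power figures.** Two-sample comparison, two-sided alpha 0.05/3, 112 per arm (Protocol 12.8.1):

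- SANDE, difference 10, SD 23: noncentrality = 10 / (23 × √(2/112)) = 3.25. Power is 0.799 (noncentral t) or 0.805 (normal), against the stated 80%.
- Staining, difference 1, SD 1: power above 0.999, against the stated figure of more than 99%.

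**4. Is staining power at risk?** The smallest n per arm with at least 99% power is 47 (0.991). The loss needed to fall to that is (112 − 47)/112 = 58%. Power remains above 0.999 at 103 per arm (112 less 8%). It is not at risk.

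**5. Possible shift in the staining effect.** No removal rate is given, so these inputs are assumptions: a fraction f of an ECF843 arm is stopped, those who stay have the planned effect of 1 point, and stopped subjects would have had r times that benefit. Stopped vehicle subjects are taken to resemble vehicle subjects who stay, and earlier visits are taken not to predict the difference. The MAR estimate is then about 1, the true arm-wide effect is 1 − f(1 − r), and the overstatement is f(1 − r) points, or f(1 − r)/(1 − f(1 − r)) in relative terms.

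| r | f = 1% | f = 8% |
|---|---|---|
| 1 (full benefit) | 0 | 0 |
| 0.5 | 0.005 (0.5%) | 0.04 (4.2%) |
| 0 (no benefit) | 0.01 (1.0%) | 0.08 (8.7%) |
| −1 (1 point worse than vehicle) | 0.02 (2.0%) | 0.16 (19%) |

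These are illustrations, not bounds.

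**6. Direction.** If both arms have informative loss, bias = f_E·d_E − f_V·d_V, where d is the later improvement of those who stay minus that of those stopped. With d = 1 in both arms:

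- 8% and 8% stopped: 0.08 − 0.08 = 0.
- 8% ECF843, 1% vehicle: 0.08 − 0.01 = +0.07.
- 1% ECF843, 8% vehicle: 0.01 − 0.08 = −0.07.

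The documents do not indicate which case applies.

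**7. Supplementary analysis.** Staining collected after a treatment stop is used. Where it is missing, ECF843 subjects are imputed by jump-to-reference (Protocol 12.4.6, SAP Table 2-5). Each such subject lowers the later effect by about 1/136 = 0.007 to 1/112 = 0.009 points, and only if that subject would otherwise have kept the full 1-point benefit. (680/5 = 136 randomized per arm; 112 planned for analysis.)

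**The case against.** The strongest reply is that this is a reasonable rule. SANDE is a daily primary endpoint, discontinuation follows only after the reason is sought and correction tried, and the Section 9 lead sentence allows stopping for non-compliance. Other rules also remove subjects: those who cannot refrain from artificial tears and cannot meet study requirements, and those who receive device therapy or punctal plugs (Protocol 6.2.2). Protocol 8 says "Missed or rescheduled visits should not lead to automatic discontinuation", but that bars only automatic stops, and 8.5.1 is not automatic. All of this stands. A reader might infer that 8.5.1 contradicts the rest of the protocol. It does not; it is a design choice.

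Three further objections also stand.

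- A reader might infer that a subject stopped after Day 14 loses Days 28, 42 and 56 from the primary analysis. The on-treatment restriction and the 28-day exposure limit rule that out for ECF843 subjects.
- A reader of the minimum-data list in 9.1.1 alone might infer that staining ends when treatment stops. The same section and the glossary make continued visits the default, so the supplementary analysis may recover it. It is only not assured.
- Protocol 5 says: "Enrollment in the study will remain open until a sufficient number of evaluable subjects is achieved in Part 1". That may replace lost numbers, although it does not correct informative loss.

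What the reply does not answer is the benefit. Stopping the subject improves no endpoint, and OTH11 already provides for poor diary compliers to stay in every analysis set.

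**Conclusion.** The point holds as a cheap improvement. The visible text leads from diary failure to a treatment stop and then to exclusion of later clinic-graded staining that does not depend on the diary. The result is avoidable missingness at site discretion, handled under MAR with no planned sensitivity analysis.

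Its size cannot be determined and is probably small. The 1 to 8% range and every value of r and d above are assumptions. Staining power is not at risk at the planned effect and SD. A reader might infer that the rule favours ECF843. The documents do not support that, since the bias can be positive, zero or negative. Nor does the point promise better SANDE data: these subjects' diaries are sparse whether or not they are stopped, so no SANDE figure is claimed.

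**What to change.** In Protocol 8.5.1, replace the final instruction with this rule: after a subject has been randomized and has started treatment, diary non-compliance alone leads to retraining, a recorded reason, and deviation OTH11 if compliance is below 50%; the subject stays on treatment and in all scheduled visits. Add a matching exception to the Section 9 lead sentence and to the protocol-requirements bullet in 9.1.1, so that neither triggers the stop by another route. Missed diary days stay missing under MAR, as already planned. Stopping for safety, withdrawn consent or any other listed reason is unchanged, and diary inability found before randomization, as in the Part 2 run-in, can still exclude a subject.

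Leave Table 8-1 footnote 3 as it is. It says "Sites will enter average SANDE score (obtained from the electronic diary", along with the staining score, at contact with the randomization system. How that entry is used, and how it relates to the undisclosed selection rules, is not visible. The sponsor can see those rules and should check whether a sparse or empty diary average needs provision there.

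The cost is three short protocol edits and a site instruction, with no change to the visible SAP text. The downside is continued visits and drug supply for a few subjects with sparse diaries. Any informative loss in SANDE itself remains unsolved.
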